Pathologic data will be obtained from the pathology reports after surgery with particular emphasis on the involvement of surgical margins with cancer, total number of lymph nodes harvested and their involvement with cancer as well as the pathologic stage of the tumor. All institutions will adopt a standardized procedure to process the cystectomy specimens along with the lymph nodes. A standardized form will be used to collect all the information pertaining to specimen processing and staging by the participating institutions. A copy of the pathologic form will be available in the patients' clinical records.

Perioperative mortality and morbidity will be evaluated using the modified Clavien grading system for complications by prospectively recording the intraoperative and post operative complications until discharge and by patient interview during post discharge period until 4-6 weeks after surgery. The above data will be separately recorded in the patient's clinical records in an inpatient and outpatient setting.

Perioperative measures such as estimated blood loss (EBL), blood transfusion rates, total intraoperative fluid requirements, total operative time, total postoperative length of hospital stay and analgesic requirement will be prospectively recorded during the surgery and the postoperative hospital stay using the anesthesia, operative, nursing and inpatient medical records by a research coordinator. All medications will be converted to morphine equivalents by using the online calculator The Clinician's Ultimate Reference found at <http://www.globalrph.com/narcoticonv.htm>

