|  |   |         |   |                 |                 |   |   |   |
|--|---|---------|---|-----------------|-----------------|---|---|---|
| Quality of Life Questionnaire (QOL) - Vanderbilt Cystectomy Index and SF8  | √ |         |   | √
(±30 days) | √
(±30 days) |   |   |   |
| Obtain Pathology Reports for Surgical Margin Status and Lymph Node Count   |   |         | √ |                 |                 |   |   |   |
| Surgical Complications per Modified Clavien Classification (AEs)/ Serious Adverse Events   |   |         | √ | √               | √               | √ | √ | √ |
| Postoperative Complication Rates (Surgeon's 90-Day Data Form)  |   |         |   | √               |                 |   |   |   |
| Imaging (CT scan /MRI /Xray/etc of Abdomen/Pelvis/Chest /etc)  | √ |         |   |                 |                 | √ | √ | √ |
| OR Costs
Hospital Costs   |   | √       |   |                 |                 |   |   |   |
| Surgeon's Intra Op Data, Cystectomy Pathology  |   | Post Op |   |                 |                 |   |   |   |
| Length of Hospital Stay, Analgesics, Complications (Surgeon's Post Op Data Form)   |   | √       |   |                 |                 |   |   |   |
| Target Lesions (Post Surgical Disease Assessment Form) to document cancer progression, according to local site Standard of Care. |   |         |   |                 | √               | √ | √ | √ |

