**Secondary Endpoints**

We will determine whether RARC is superior to ORC in terms of blood loss. More specifically, the overall blood loss due to surgery will be compared between the two treatment arms. In the ORC group the average blood loss is 575 ml . 288 patients yield 90% power to detect a difference of blood loss between the two treatment groups of 20%. These calculations are based on the assumption that the amount of blood loss is normally distributed, that the average blood loss in the open surgery group is 575ml, and that the standard deviation of blood loss is 300ml. A one-sided significance level of 0.025 was used.

We will determine whether RARC is superior to ORC in terms of transfusion rates. The transfusion rates (proportion of patients requiring blood transfusions) will be compared between the two treatment arms. The transfusion rate for ORC is approximately 75%(from Table 2, unpublished). 288 patients yield 92% power and a one-sided significance level of 0.025 to detect a difference of transfusion rates between arms of at least 20%. These calculations are based on the assumption that the transfusion rate is binomially distributed.

*Table 2 (Preliminary Data from University of Texas Health Sciences Center, San Antonio)*

|  | ORC (n=12)  | RARC(n=12)      | p-value |
|--|-------------|-----------------|---------|
| Median (IQR) Units of Blood Given | 2.5 (1-5)   | 0 (0-3)         | 0.082   |
| Transfusion given (%)             | 9/12 (75%)  | 4/12 (33%)      | 0.041   |
| Median (IQR) LOS (days)           | 6.5 (6-8.5) | 6.5 (5-9.5)     | 0.554   |
| LOS (5 days or less)              | 0/12 (0%)   | 4/12 (33.3%)    | 0.028   |
| Median No. LNs (IQR)              | 19 (6-27)   | 10.5 (8.5-17.5) | 0.30    |
| Positive margin                   | 3/12 (25%)  | 0/12 (0%)       | 0.064   |

*All positive margins in the ORC group had pT4 disease.*

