Length of hospital stay will be used as a surrogate for recovery after surgery. We will determine whether RARC is superior to ORC in terms of length of hospital stay. Currently, all of the patients receiving ORC stay in the hospital for more than 5 days while 67% of patients in the RARC group stay in the hospital for more than 5 days (from Table 3, unpublished). 288 patients yield 97% power and a one-sided significance level of 0.025 to detect a difference in percent of patients requiring a hospital stay beyond 5 days between RARC and ORC arms of at least 20%. These calculations are based on the assumption that the percent patients requiring a hospital stay beyond 5 days is binomially distributed.

Table 3 (Preliminary Data for Cost Analyses from University of North Carolina)

|                          | ORC (n=21) | RARC (n=20) | P VALUE                |
|--------------------------|------------|-------------|------------------------|
| Age (median)             | 70         | 70          |                        |
| OR time (mins)           | 293        | 389         | <0.001                 |
| OR fees (dollars)        | 5441       | 6202        | <0.00001               |
| OR disposables (dollars) | 2485       | 3715        | = 0.0003               |
| OR capital + reusables   | 50         | 2000        |                        |
| LOS (days)               | 6          | 4           | =0.02(mann whitney U)  |
| Room and Board           | 5954       | 3664        | =0.005 (mann whitneyU) |
| Overall Costs            | 19047      | 19837       | =0.14(mann whitney U)  |

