### **Special Precautions**

Subject data will be examined at each follow up visit and subjects queried for adverse events (AE) defined as complications related to the robotic/open cystectomy and/or study procedures. An AE or complication is the appearance of undesirable sign(s), symptom(s), or medical condition(s) occurring after a participant signs the informed consent and considered to be related to the robotic/open cystectomy and/or study procedure. A serious adverse event is any untoward medical occurrence that:

1. Is fatal or life-threatening
2. Requires hospitalization or prolongation of existing hospitalization
3. Results in disability/incapacity
4. Is medically significant in that it may jeopardize the patient and may require medical or surgical intervention to prevent one of the outcomes listed above.

All AEs or complications will be graded for severity according to the modified Clavien grading system. All adverse events will be reported to the IRB at the time of annual review and to the DSMC as described below.

The investigator is obligated to assess the relationship between any study-related procedure and the occurrence of each SAE. The investigator will use clinical judgment to determine the relationship. Alternative causes, such as natural history of the underlying diseases, concomitant therapy, other risk factors, and the temporal

relationship of the event to any study-related procedure will be considered and investigated.

Even in situations when an SAE has occurred and the investigator has incomplete information to include in the initial SAE report, the investigator will make an assessment of causality for every event prior to reporting it. The investigator may change his opinion of causality in light of follow-up information and amend the SAE case report form and report accordingly.

SAEs meeting the IRB definition of Unanticipated Problems Involving Risk to Subjects or others (UPIRSO) will be reported to the IRB within 7 days, and within 48 hours if life-threatening or fatal or will follow the guidelines as required by the local IRBs.

All SAEs will also be reported to the coordinating center office of [name] at the University of Miami. After completion of review by [name], SAEs will be summarized and communicated across sites via the posting to the study website at <https://prodq.crab.org/[name]/Login.aspx>.

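### Analgesic requirement is totalled only to discharge, and RARC is expected to bring earlier discharge, so the total mixes discharge timing with analgesic need

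*Combined protocol and SAP*

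**What the plan says.** Section 3 lists analgesic requirement and transfusion among the perioperative measures in Specific Aim 2, item 5. Section 4, under Submission and processing of specimens, sets the recording period. The sentence begins "Perioperative measures such as estimated blood loss (EBL), blood transfusion rates, total intraoperative fluid requirements, total operative time" and continues "total postoperative length of hospital stay and analgesic requirement will be prospectively recorded during the surgery and the postoperative hospital stay". The sources are the anesthesia, operative, nursing and inpatient records, and medications are converted to morphine equivalents.

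The study calendar (Table 1) agrees. The row "Length of Hospital Stay, Analgesics, Complications (Surgeon's Post Op Data Form" is ticked only in the hospital discharge column.

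Complications are treated differently. They are followed after discharge "by patient interview during post discharge period until 4-6 weeks after surgery", and the calendar has a separate row, "Postoperative Complication Rates (Surgeon's 90-Day Data Form", at 3 months. Both apply equally to the two arms.

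Section 5, Secondary Endpoints, plans to show that RARC is superior on length of stay: "Length of hospital stay will be used as a surrogate for recovery after surgery". It also plans a powered, one-sided transfusion comparison: "The transfusion rates (proportion of patients requiring blood transfusions) will be compared between the two treatment arms". It gives no summary measure, test or power for analgesic requirement.

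**The concern.** For a quantity that accumulates over time, the observation period should not depend on treatment. Here it ends at discharge, which the trial itself expects to come earlier in one arm. Opioids given on days 5 and 6 count for an ORC patient still on the ward. The same need in a RARC patient who went home on day 4 is not recorded.

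Section 2 names lower opioid requirement as a purported advantage of RARC that lacks randomised evidence. A lower total to discharge could not settle that question, because it could arise from earlier discharge alone. Perioperative care follows each institution's own policy, so no common discharge rule makes the two periods comparable.

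**Working it through.** **Inputs from the documents.** Length of stay is 6 days (ORC) v 4 days (RARC) in Table 3; the table does not say whether these are means or medians. Table 2 gives medians of 6.5 v 6.5 days. There are 144 evaluable patients per arm. The ORC transfusion rate is 75%. The documents give no daily opioid use, no variability of opioid use and no transfusion timing, so those are assumed below.

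**Step 1: analgesic total.** Suppose daily need is identical in the two arms and each day's use is a fraction r of the day before. The total over L days is proportional to (1 − r^L)/(1 − r), or L if r = 1. The recorded RARC:ORC ratio is (1 − r^4)/(1 − r^6).

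| r | Total, 4 days | Total, 6 days | Ratio | RARC appears lower by |
|---|---|---|---|---|
| 1 | 4.000 | 6.000 | 0.667 | 33% |
| 0.85 | 3.187 | 4.152 | 0.767 | 23% |
| 0.8 | 2.952 | 3.689 | 0.800 | 20% |
| 0.7 | 2.533 | 2.941 | 0.861 | 14% |
| 0.6 | 2.176 | 2.383 | 0.913 | 9% |
| 0.5 | 1.875 | 1.969 | 0.952 | 5% |

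With equal stays, as in the Table 2 medians, the ratio is 1 and the artefact is 0%.

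**Step 2: could it produce a spurious difference?** The plan states no analgesic test, so this is an illustration. For a one-sided 0.025 comparison of means, the chance of declaring RARC better when need is identical is Φ(δ/(CV × √(2/144)) − 1.96). Here δ is the apparent reduction and CV is the assumed coefficient of variation, taken from 0.5 to 1.5.
- δ = 0.333: above 99% at CV 0.5, and 47% at CV 1.5 (0.333/0.177 − 1.96 = −0.07).
- δ = 0.087: 31% at CV 0.5, and 7% at CV 1.5.

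All exceed the nominal 2.5%.

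**Step 3: does dividing by days repair it?** The per-day ratio is the total ratio × 6/4. At r = 1 it is 1.00, but at r = 0.7 it is 0.861 × 1.5 = 1.29 and at r = 0.5 it is 0.952 × 1.5 = 1.43. When use tapers, the average per inpatient day errs against RARC, because a short stay consists of the high-use days. It can support a fixed-window comparison but not replace it.

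**Step 4: transfusion.** The plan states 92% power for a 20-point difference from 75%. With 75% v 55%, 144 per arm and one-sided 0.025, the usual pooled formula gives 94.9%, or 93.4% with continuity correction, which is close to the stated figure. Now let the true rate be 75% in both arms, and let a fraction q of transfused patients have their first transfusion after day 4. Suppose these are recorded for ORC and missed for RARC, so the observed RARC rate is 0.75 × (1 − q).

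| q | Observed RARC rate | Chance of a false one-sided finding |
|---|---|---|
| 0 | 75% | 2.5% |
| 2% | 73.5% | 4.8% |
| 5% | 71.3% | 10.7% |
| 10% | 67.5% | 28.9% |

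The documents do not say which value of q applies, and zero is possible.

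**The case against.** The strongest reply on analgesics is that Section 5 never says an unscaled total will be compared, so what is missing may be only an analysis definition. It is true that no one-sided analgesic test is planned, and none should be attributed to the trial. But the data are collected to discharge and converted to morphine equivalents without a window. The natural alternative, use per inpatient day, is itself distorted by tapering (step 3). The window therefore has to be chosen deliberately.

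A second reply is that the evidence for earlier discharge is mixed. This stands in part. Table 2 shows equal medians (p = 0.554) and a longer upper quartile for RARC (9.5 v 8.5 days), although 4/12 RARC v 0/12 ORC patients had stays of 5 days or less. On Table 2 alone, the direction of any artefact is uncertain.

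A reader might infer two stronger things that the documents do not support.
- **That length of stay is biased in the same way.** It is not. Stay is the outcome itself, ends at discharge by definition and is fully observed in both arms. How readmission or early in-hospital death counts towards staying beyond 5 days is not stated, but that is a question of endpoint definition. Readmissions are not ignored elsewhere: the serious adverse event criteria include "Requires hospitalization or prolongation of existing hospitalization".
- **That the transfusion test will miss events unequally.** This is possible but not shown. The outcome is yes/no and the recording period includes the operation, so only a first transfusion after an earlier discharge matters. The form mock-ups are not reproduced in the document, so whether the 90-day form captures later transfusions cannot be judged.

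**Conclusion.** The point holds for analgesic requirement. Recorded as planned, the total mixes discharge timing with need. If stays are 4 v 6 days and daily need is identical, RARC would appear about 5% to 33% lower. The upper end requires constant daily use and the lower end a halving each day. If stays are equal, the artefact is nil. The taper and the CV are assumptions.

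For transfusion, the open window is a secondary matter of unknown size. For length of stay, there is no observation-time bias. The primary two-year progression-free survival comparison is unaffected, so this concerns how a perioperative comparison is read and not the trial's main conclusion.

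**What to change.** 1. **Analgesics.** Define the measure as total morphine equivalents over a fixed period from surgery, the same in both arms and lying within nearly every stay, for example the first 72 hours. Report use per inpatient day as supportive only. State in advance how patients who leave or die before the period ends are handled, and report their number by arm. The pilot tables do not give the share of stays shorter than 72 hours, so confirm the length of the window from pooled data without reference to arm.
2. **Transfusion.** State one window from surgery that is identical in both arms. If it extends beyond the index stay, say which form captures later transfusions. A long window such as 90 days would change the question by including transfusions unrelated to the operation, and the 75% planning rate and 92% power might then no longer apply.

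The analgesic change uses inpatient records already being abstracted. Its costs are slightly more abstraction, because doses must be tied to time since surgery, and no information on later use. The transfusion change needs wording only, unless the chosen window requires capture after discharge. Neither changes the sample size or the primary analysis.

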### Costs

We will obtain fixed and variable operating room costs by assessing amortized cost of robotic machine per case, amortized cost of maintenance per case, costs of dispensable equipment, cost of OR personnel and anesthesia resources per time. We will also obtain fixed and variable hospital costs based on length of stay. The above cost data will be collected from each participating center and data will be stored and analyzed by CRAB. We hypothesize that costs associated with robotic surgery will be no more than 5% of the costs associated with ORC.

Only research personnel who are approved by the IRBs of the participating institutions will have access to study research information. All participating investigators are required to undergo and maintain CITI training.

**Clinical Procedures**  
Measurements of Study Endpoints

Measurements of the study end points will be conducted according to the following Table 1:

Table 1: Study Calendar

| Assessment  | Baseline
(Preoperative)          | Hospital
Discharge
(±2 weeks) | 4-6
Weeks    | 3
months     | 6
months     | 12
months | 24
Months | 36
Months |
|---|-------------------------------------|-------------------------------------|-----------------|-----------------|-----------------|--------------|--------------|--------------|
| Baseline History and Physical Exam, Consent, Screening, ECOG Performance Status, TURBT findings | √                                   |                                     |                 |                 |                 |              |              |              |
| Randomization   | √ (within 60 days prior to surgery) |                                     |                 |                 |                 |              |              |              |
| Progression Free Survival   |                                     |                                     |                 |                 |                 | √            | √            | √            |
| Overall Survival  |                                     |                                     | √               | √               | √               | √            | √            | √            |
| Activities of Daily Living (ADL) score  | √                                   |                                     | √
(±30 days) | √
(±30 days) | √
(±30 days) |              |              |              |
| Instrumental Activities of Daily Living (IADL) score  | √                                   |                                     | √
(±30 days) | √
(±30 days) | √
(±30 days) |              |              |              |
| Hand Grip Strength Test   | √                                   |                                     | √
(±30 days) | √
(±30 days) | √
(±30 days) |              |              |              |
| Timed Up and Go Walking Test  | √                                   |                                     | √
(±30 days) | √
(±30 days) | √
(±30 days) |              |              |              |
| Hemoglobin, BMP, serum albumin  | √                                   |                                     | √               | √               | √               | √            | √            | √            |

|  |   |         |   |                 |                 |   |   |   |
|--|---|---------|---|-----------------|-----------------|---|---|---|
| Quality of Life Questionnaire (QOL) - Vanderbilt Cystectomy Index and SF8  | √ |         |   | √
(±30 days) | √
(±30 days) |   |   |   |
| Obtain Pathology Reports for Surgical Margin Status and Lymph Node Count   |   |         | √ |                 |                 |   |   |   |
| Surgical Complications per Modified Clavien Classification (AEs)/ Serious Adverse Events   |   |         | √ | √               | √               | √ | √ | √ |
| Postoperative Complication Rates (Surgeon's 90-Day Data Form)  |   |         |   | √               |                 |   |   |   |
| Imaging (CT scan /MRI /Xray/etc of Abdomen/Pelvis/Chest /etc)  | √ |         |   |                 |                 | √ | √ | √ |
| OR Costs
Hospital Costs   |   | √       |   |                 |                 |   |   |   |
| Surgeon's Intra Op Data, Cystectomy Pathology  |   | Post Op |   |                 |                 |   |   |   |
| Length of Hospital Stay, Analgesics, Complications (Surgeon's Post Op Data Form)   |   | √       |   |                 |                 |   |   |   |
| Target Lesions (Post Surgical Disease Assessment Form) to document cancer progression, according to local site Standard of Care. |   |         |   |                 | √               | √ | √ | √ |

## Data Submission Procedures

### Data must be submitted according to the following schedule:

- To perform randomization and obtain subject ID number: *Randomization Form.*
  
- Within 1 week following enrollment: All of the following forms:
  - *Medical History Form*
  - *Surgical History Form*
  - *Findings at TURBT Form*
  - *Hemoglobin, BMP, and Serum Albumin Form*
  - *Screening Physical Exam and Vital Signs Form*
  - *Baseline Disease Assessment Form*
  - *Baseline Vanderbilt Cystectomy Index QOL Questionnaire*
  - *Baseline SF-8 QOL Questionnaire*
  - *Baseline Activities of Daily Living QOL Questionnaire*
  - *Baseline Activities of Instrumental Activities of Daily Living QOL Questionnaire*
  - *Baseline Hand Grip Strength Form*
  - *Baseline Timed Up and Go Walking Test Form*
  
- Within 1 week of each post-surgery laboratory assessment per Table 1:
  - *Hemoglobin, BMP, and Serum Albumin Form*
  
- Within 1 week following surgery: *Surgeon's Intra-Op Data Form.*
  
- Within 1 week following discharge for surgical hospitalization:
  - *Hospital Discharge Visit: OR and Hospital Costs Reporting Form*
  - *Surgeon's Post-Op Data Form*
  
- Within 1 week of each scheduled ADL, IADL, and QOL assessment per Table 1:
  - *Vanderbilt Cystectomy Index QOL Questionnaire*
  - *SF-8 QOL Questionnaire*
  - *Activities of Daily Living QOL Questionnaire*
  - *Activities of Instrumental Activities of Daily Living QOL Questionnaire*
  - *Hand Grip Strength Form*
  - *Timed Up and Go Walking Test Form*
  
- Within 2 weeks following each scheduled disease assessment/imaging exam per Table 1: *Post Surgical Disease Assessment Form.*
  
- Within 4-6 weeks post-op: *Cystectomy Pathology Form*
  
- Within 1 week following 90-days post-op: *Surgeon's 90-Day Data Form*
  
- Within 1 week following 6-, 12-, 24-, and 36 months post-op (respectively):

- *Post Surgical Disease Assessment*
  - *Hematology Form*
  - *Serum Chemistry Form*
- Within 1 week following each scheduled adverse events evaluation (per Table 1) until adverse events have resolved. Adverse event information is collected on the *Surgical Complications-Adverse Events Form*.
  - Within the time frame and per the guidelines specified in section 6: *Serious Adverse Events*. Report per the instructions provided in section 6 AND flag as “SAE” on the *Surgical Complications-Adverse Events Form*.
  - Within 2 weeks following knowledge of death, if death occurs prior to end of study: *Death Report Form*.

